Randomized Study Of Novel Enuresis Alarm (GoGoband®)Vs Standard Bedwetting Alarm

Protocol Number
2000031281

NCT05214131

Protocol Version
February 20, 2024
Version #6

IDE Number:

IDE Holder:

PRINCIPAL INVESTIGATOR:

[name]., Ph.D.
Department of Urology
[contact]
Email Address: [contact]

Confidentiality Statement:

2000031281

February 20, 2024

REVISION HISTORY:

Include the IRB approved protocol version number and date for each revision of the protocol. All version history should remain in the table and never be deleted. The oldest IRB approved version of the protocol should be listed on the top row. The most recent IRB approved version should be listed on the bottom row.

Revision #	Version Date
1	Sept 1 2021
2	Sept 9 2021
3	November 18, 2021
4	December 28, 2021
5	Jan 15 2022
6	February 20, 2024

2000031281

February 20, 2024

Synopsis

Primary Objective
 
Identify the dry night rate in patients using the GoGoband® nocturnal enuresis device vs a standard Pflaunger bedwetting alarm.

Secondary Objective (if applicable)
 
to ascertain if familial incidence of nocturnal enuresis has an effect on outcomes

Study Duration: total 3 years, 2 years active with 1 year for analysis

Study Design
 
Include a high-level description of the study design.
 
This is a prospective randomized comparison of GoGoband® vs standard nocturnal enuresis alarm

Number of Study Sites
 
Study sites will include all clinic sites where patients are seen in the Yale New Haven Health System
 
Yale New Haven Children’s Hospital clinic WP2 Yale New Haven Children’s Hospital Longwharf Clinic Yale New Haven Children’s Hospital Trumbull clinic Yale New Haven Children’s Hospital Norwalk clinic Yale New Haven Children’s Hospital Greenwich Clinic


Study Population
 
Define the study population, source of the participants, and selection rationale. Study subjects should be representative of the population of interest. Provide a brief description of the study population (e.g., healthy/sick, children/adult, inpatient/outpatient, demographic groups), the characteristics of different study groups, if applicable, and the source of participants. Do not list inclusion/exclusion criteria here, as these will be listed in the upcoming sections.
 
Study population will consist of children seen in our Bladder and continence program who present with nocturnal enuresis. Patients will be evaluated with validated questionnaire to confirm that they are monosymptomatic nocturnal enuretics and will be asked if they wish to participate in the study if they are between 6 yrs and 21 years of age.

Number of Participants: 150 children and adolescents

Primary Outcome Variables

2000031281

February 20, 2024

Variables:

Wetting event: Dry or Wet

Did patient wear the device: yes or no used to measure compliance

Is the patient considered cured (dry 29/30 nights) : yes or no

Is the patient partially better (improvement of 50% or more compared to pre treatment)

Did the patient show no improvement (<50% improvement compared to Pre treatment)

Secondary and Exploratory Outcome Variables (if applicable)

Did parents wake to assist child when alarm goes off: yes or no (2 nd measure of compliance)

What is the role of parental assistance in Dry night rates

Is there a correlation with parental NE and response to alarm

2000031281

February 20, 2024

Abbreviations

Abbreviation	Explanation
MNE	Mono symptomatic nocturnal enuresis
NMNE	Non Mono symptomatic nocturnal enuresis
SNEA	Standard Nocturnal enuresis Alarm
DV	Dysfunctional Voiding
DVQ	Dysfunctional Voiding questionnaire
PPG	Photoplethysmography

Glossary of Terms

Glossary	Explanation
----------	-------------

Table of Contents

Preface.....	2
Synopsis	4
Primary Objective.....	4
Secondary Objective (if applicable).....	4
Study Duration.....	4
Study Design	4
Number of Study Sites.....	4
Study Population	5
Number of Participants.....	5
Primary Outcome Variables	5
Secondary and Exploratory Outcome Variables (if applicable).....	5
Abbreviations	6
Glossary of Terms	7
1 Introduction.....	11
1.1 Introductory Statement	11
2 Background.....	12
2.1.1 Device Preclinical Experience	12
2.1.2 Device Clinical Experience.....	12

1.1 Introductory Statement

This document is a protocol for a human research study. The purpose of this protocol is to ensure that this study is to be conducted according to ICH GCP guidelines, and according to CFR 21 Part 812, other applicable government regulations, and Institutional research policies and procedures.

2 Background

2.1.1 Device Preclinical Experience

GoGoband® is a new biometric, artificial intelligence and machine learning powered wearable bedwetting alarm that uses Pavlovian or classical conditional training to increase the effectiveness of enuresis alarm treatment. This is accomplished with the use of heart rate data, heart rate variability (HRV) analysis and real time monitoring that combines the use of algorithms developed with machine learning to learn the individual profile of each patient. Each device consists of a photoplethysmography (PPG) heart rate sensor worn on the calf, a bedside tablet, a Bluetooth moisture sensor and a parent app. The first 7-10 wetting episodes are utilized to develop the individualized program based on HRV data to predict when an impending urination event is going to happen. Artificial intelligence in our web-based database develops hundreds of thousands of models and selects the best one to predict a urination event. As time moves along the machine learning continues to modify the signaling parameters as the child's bedwetting improves. In the weaning phase the system gradually eliminates alarming episodes in a controlled fashion and as the children continues to progress it will eliminate all alarming. Once this stage is completed and the child remains dry for a week consecutively, they are deemed cured. This process can last a few days to several months with some children using the alarm remaining dry on day one and never having another accident without the alarm going off and others remain in need of the system to continue to wake them and keep them dry.

Our most recent data indicates that we can achieve a dry night rate as high as 94% in compliant patients that use the device at least 80% of the time. these results are in stark contrast to the best reported outcomes of 70% in European SNEA studies.

In summary the GoGoband® is a new biometric, artificial intelligence and machine learning powered wearable bedwetting alarm that uses Pavlovian or classical conditional training to increase the effectiveness of enuresis alarm treatment. The non-intelligent alarms on the market today rely on a form of operant conditioning which in many cases relies on negative reinforcement i.e. waking the child up to change the bed or do their laundry.

2.1.2 Device Clinical Experience

Data to be presented at the American urological association meeting scheduled for Sept 10, 2021 based on quality Improvement study

Abstract ID: 21-3995

Abstract Title: A Novel Bedwetting Alarm Utilizing Real Time Heart Rate Analysis and Artificial Intelligence to Wake Patients Prior to Wetting: Preliminary Outcomes

Presenting Author: [name]

Session Details

Type: Podium - PD15

Title: Pediatric Urology I

Date: Friday, September 10, 2021

Time: 3:30 PM - 5:30 PM

Building: Venetian-Sands Expo Center

Room: Marco Polo 804

A copy of the abstract is attached below

21-3995

A NOVEL BEDWETTING ALARM UTILIZING REAL TIME HEART RATE ANALYSIS AND ARTIFICIAL INTELLIGENCE TO WAKE PATIENTS PRIOR TO WETTING: PRELIMINARY OUTCOMES

[name]*, New Haven, CT, [name], [name], [name], Ashland, VA

INTRODUCTION AND OBJECTIVE: Bedwetting alarms (BWA) have been around for more than half a century with little innovation in the field. GOGOBand® utilizes real time heart rate variability (HRV) analysis and applied artificial intelligence (AI) to create an alarm that is capable of waking the patient up prior to wetting. Our Aim was to evaluate the efficacy the new Smart GoGoBand®.

METHODS: Data was retrieved and analyzed from our servers, of patients who purchased the GOGOBand® which includes a heart rate monitor, moisture sensor, bedside tablet and app for the parents phone in this study. There are 3 modes, training; where the individualized HRV parameters are used to build the alerting model. Once patients are done with training, they enter the Predictive mode where they receive an alarm if an impending urination event is noted. In Weaning mode the alerting is gradually suppressed. Only patients that used the alarm for more than 30 days were included. Data analysis was done with SPSS and xistat.

RESULTS: A total of 40 subjects that have used the system for more than 30 nights were included in this analysis. Gender mix was 33 males (82.5%) and 7 females (17.5%). The mean age of the subjects is 10.6 yrs. Subjects wet the bed an average of 6.2 nights per week prior to treatment. Severity and number of accidents per night had no impact on the ability to achieve dryness with the GOGO Band® device in logistical regression analysis. The data was also segregated based on compliance since it became clear during the analysis that compliant patients achieved better results than non-compliant patients.

[figure not shown]
Mode	% dry with <65% compliance	% dry with 65-80% compliance	% dry with >80% compliance	Total nights
Training	17.6 ^a	71.6 ^b	10.8 ^c	251
Predictive	80.2 ^a	78.6 ^b	93.8 ^b	760
Weaning	80.6 ^a	86.8 ^b	92.9 ^b	1460
Total	80.4 ^a	81.9 ^a	92.1 ^b	2451

Each different letter superscript in each row denotes a statistically different outcome (p<0.05).

The figure depicts the degree of predictive alarming and the patient's ability to stay dry. It is clear that the high compliance patients (green dots) have less alarming events indicating that the system is just not functioning randomly but the machine learning algorithm has learned to sense when an accident is impending.

CONCLUSIONS: Our findings indicate that the GOGOBand® in high compliance patients has a 93% dry night rate that surpasses standard alarms. The data indicates that there are physiological changes which lead to a change in bladder-brain processing that allows for the patient to sleep through the night and not wet themselves.

Source of Funding: NONE

More recent data which includes 60 patients yet to be presented indicates that success rates are higher during the weaning phase

[Print this Page for Your Records](#)

[Close Window](#)

Control/Tracking Number: 2021- A- 519- SPU
Activity: Abstract
Current Date/ Time: 7/26/2021 9:51:45 PM

Analysis of 60 patients treated with the GoGoBand AI Powered Bedwetting Alarm

Author Block: [name], MD¹, [name], MBA,² [name], MBA,BSE³, [name], MBA,BSE³, [name], BSE³.
¹Yale University, New Haven, CT, USA, ²GoGoBand, Ashland, VA, USA, ³Gogoband, Ashland, VA, USA.

Abstract:

BACKGROUND: Bedwetting alarms (BWA) have been around for more than half a century with little innovation in the field. GOGOBand® utilizes real time heart rate variability (HRV) analysis and applied artificial intelligence (AI) to create an alarm that is capable of waking the patient prior to wetting. Our Aim was to evaluate the efficacy continues to remain high with the addition of 20 new patients to our servers. **METHODS:** Data was retrieved and analyzed from our servers, of patients who purchased the GOGOBand® which includes a heart rate monitor, moisture sensor, bedside tablet and app for the parents phone in this study. There are 3 modes, training, where the individualized HRV parameters are used to build the alerting model. Once patients are done with training, they enter the Predictive mode where they receive an alarm if an impending urination event is noted. In Weaning mode the alerting is gradually suppressed. Only patients that used the alarm for more than 30 days were included. Data analysis was done with SPSS and xlstat. **RESULTS:** A total of 60 subjects that have used the system for more than 30 nights were included in this analysis. Gender mix was 46 males (76.6%) and 14 females (23.3%). The mean age of the subjects is 10.2 yrs. Subjects wet the bed an average of 6.2 nights per week prior to treatment. Severity and number of accidents per night had no impact on the ability to achieve dryness with the GOGO Band® device in logistical regression analysis. The data was also segregated based on compliance since it became clear during the analysis that compliant patients achieved better results than non-compliant patients. A crosstab analysis was performed and is reported in table 1. The data clearly indicates that compliant patients >80% are able to remain dry 96% of the time once they enter the weaning phase. **CONCLUSIONS:** Our findings indicate a 96% success rate in patients that are weaning, this translates to 1.2 wet nights per 30 days. This compares to the same group when starting the use of the alarm had only 14.4 dry nights per 30 days. The addition of the 20 patients indicates that that our results are enduring and seem to be improving as we continue to increase the number of patients that are on the system.

compliance groups		training	predictive	Wean	Total	
<=65%	dry	Count	311 _a	881 _b	1584 _c	2776
		% within group	59.70%	77.30%	87.50%	80.00%
	wet	Count	210 _a	258 _b	226 _c	694
	% within group	40.30%	22.70%	12.50%	20.00%	
>=65 and <=80%	dry	Count	92 _a	240 _a	228 _b	560
		% within group	70.80%	71.90%	86.00%	76.80%
	wet	Count	38 _b	94 _b	37 _b	169
	% within group	29.20%	28.10%	14.00%	23.20%	
>=80%	dry	Count	26 _a	490 _b	145 _b	661
		% within group	48.10%	91.10%	96.00%	89.00%
	wet	Count	28 _b	48 _b	6 _b	82
	% within group	51.90%	8.90%	4.00%	11.00%	

Same subscript letter denotes a subset whose column proportions do not differ significantly from each other at the .05 level.

Author Disclosure Information:

- [name],**
GoGoBand Management position, Chief Science Officer.
 - [name],**
Gogoband Employment, Management position, CEO.
 - [name],**
Gogoban Employment, Management position, COO.
 - [name],**
Gogoban Employment, Management position, COO.
 - [name],**
gogoband Employment, Management position, Chief Technology Officer.
- Category (Complete):** Bowel/ Bladder Dysfunction/ Urinary Tract Infection/ Vesicoureteral Reflux
Presentation Preference (Complete): Podium Presentation

2.2 Background/prevalence of research topic

Urologic literature recognizes that enuresis alarm treatment for nocturnal enuresis is a form of behavioral therapy. It works in conjunction with both positive reinforcement and aversive negative experiences and has been shown to be effective after Mowrer and Mowrer introduced it in 1938. Unfortunately, the literature, using the current effectivity standard of maintaining four weeks of dry nights criteria from the International Children's Continence Society consensus document, reveals that it is not as effective as it is stated. Using the new standard, there are few publications that have success rates that exceed 50%^{2,3}. When the published abandonment rates (~30%) and relapse rates (~50%) are taken into consideration, the effectivity of current enuresis alarm treatment is further reduced to only 25-33%. Innovation in enuresis alarm treatment for pediatric enuresis has been stagnate for the last 30 years and clearly a better method of enuresis alarm treatment in children is necessary.

There is evidence that there is a disequilibrium in the sympathetic/parasympathetic balance in enuresis subjects utilizing heart rate variability (HRV) monitoring⁴⁻⁶. For urination to occur there must be a deactivation of the sympathetic and activation of parasympathetic flow. There are numerous other studies indicating that subjects with bladder over-activity also have a predominance of low frequency signals based on HRV analysis.⁷⁻⁹ This data coincides with our own pilot work where we have seen that an HRV spike is evident prior to an enuresis event. We therefore hypothesis that there should be a predictable change in HRV parameters that signal sympathetic/parasympathetic activity and balance, utilizing real time monitoring of subjects with nocturnal enuresis prior to an accidental voiding event. Our modeling indicates that we can predict an event by identifying an changes in heart rate as well as ultra-low frequency HRV signal utilizing signal processing in a patented method that allows for the real-time analysis of HRV to identify these specific signals. Artificial intelligence in our web-based database develops hundreds of thousands of models and selects the best one to predict a urination event. As time moves along the machine learning continues to modify the signaling parameters as the child's bedwetting improves. In the weaning phase the system gradually eliminates alarming episodes in a controlled fashion and as the children continues to progress it will eliminate all alarming. Once this stage is completed and the child remains dry for a week consecutively, they are deemed cured. This process can last a few days to several months with some children using the alarm remaining dry on day one and never having another accident without the alarm going off and others remain in need of the system to continue to wake them and keep them dry.

3 Rationale/Significance

3.1 Problem Statement

At the present time we have no side-by-side comparison studies of GoGoband® vs SNEA. Since many of the prior studies were conducted using variable outcome parameters that makes direct comparisons of studies difficult it would be beneficial to obtain comparable data from the 2 groups and compare dry night rates for the 2 devices.

3.2 Purpose of Study/Potential Impact

Our preliminary quality improvement data indicates that the GoGoband® is more efficacious than both medication and SNEA in an uncontrolled environment when deidentified data was analyzed off our servers. Our present database does not allow us to discern if patients are MNE or NMNE. Without this ability as well as for controlling for behavioral and academic problems which are known to affect outcomes in nocturnal enuresis studies, we are not able to compare our results definitively and accurately to other treatment modalities.

3.2.1 Potential Risks

Risks associated with the alarms:

- The risk of electric shock is minimal since the whole system is a battery operated low voltage system, the only part in contact with the patient is a heart rate monitor which is an approved Photoplethysmography (PPG). PPG technology is presently ubiquitous today in most smart watches and heart rate monitors. Similarly, the risk of shock from detachment of the wired ends in the regular alarm is minimal since it is low voltage battery system.
- As the device is being installed and during usage, cord entanglement is a possibility, and mitigated by wearing a shirt over the cord.
- Choking can be a hazard if any of the associated components are placed in the mouth. The age for this study is 6 or above which would minimize this risk, additionally we do not allow for the enrollment of children with developmental or behavioral disabilities which should further minimize this risk.
- If the user chooses to attach the alarm unit using a safety pin, use of a secure pin that does not come loose easily will mitigate this risk.
- The child may become disoriented by the sound of the alarm. To mitigate this a soft rug or padding at the bedside will help prevent injury should your child roll out of bed upon awakening. Minimizing the elevation of the bed above the floor is advisable.
- There may be no benefit from either alarm therapy
- Some children may be startled by the alarm and may not wish to continue to use the device, if so, they will exit the study.
- There is a risk that internet service at the home may be inadequate for proper functioning of the GoGoband® alarm, if so, they will need to exit the study.

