5.3.2 Eligibility Criteria/Vulnerable Populations

In order to be eligible to participate in this study, an individual must meet all of the following criteria:

1. Provision of signed and dated informed consent form
2. Stated willingness to comply with all study procedures and availability for the duration of the study

3. Male or female, aged 6 to 21 years
4. In good general health as evidenced by medical history and diagnosed with MNE
5. Ability to and be willing to adhere to the treatment regimen.
6. Subjects to be eligible for the Trial need to have functioning WiFi at home utilizing a home network and not a cellular tethering connection.

An individual who meets any of the following criteria will be excluded from participation in this study:

1. No patient may have had treatment of MNE in the past 6 months whether with medications or alarms
2. Current use of on ADHD medications, Tricyclics, SSRI's, NRI's or any antipsychotic medications.
3. Presence of Autistic Spectrum disorder, ADHD, genetic syndrome associated with developmental or learning disabilities
4. Treatment with another investigational drug or other intervention within last 6 months
5. Any form of Diabetes Mellitus or Diabetes Insipidus
6. No patient with known Chronic renal disease with moderate to severe renal impairment (defined as a creatinine clearance below 50mL/min).
7. No patient with known hyponatremia or a history of hyponatremia.

6 Methods

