6.1.2 Device Administration and Schedule

SNEA: Device Will be provided to the patient

1. Instruction will be provided on how to set up the device and use it
2. The device will be worn consecutively for 3 months.
3. The alarm use will be terminated if they have been dry for 3 months consecutively.

GoGoband®: Device Will be provided to the patient

1. Instruction will be provided on how to set up the device and use it
2. The device will be worn consecutively for 3 months
3. The device will follow the built in algorithm in the device to decide when to begin the weaning process.
4. The weaning process will occur automatically until there no more nights in which the system will sound impending urination alarms

Non-compliant patients will be removed from the study. Alarms will not be requested back from the participants.

Reasons for noncompliance will be the following

1. Not taking medication
2. Not using device
3. Not filling in and submitting biweekly logs.

If a bedwetting alarm breaks or is nonfunctional the device will be replaced, and the study will proceed from the last active day

Method of Assignment/Randomization (if applicable)

2000031281

February 20, 2024

Randomization will be accomplished by having 100 envelopes with 50 SNEA and 50 GoGoband® choices. The envelopes will be distributed to the sites and pulled randomly at each site.

Age matching:

After 50% enrollment in any group the average age and standard deviation of the group will be calculated and an effort to adjust enrollment so groups are age matched will be made.

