3.2.5 Biomarkers (if applicable)

3.3 Study Procedures

3.3.1 Study Schedule

Total study time is 3 months exclusive of prestudy visit which should be within 2 months of start of study.

Prestudy entry:

- all Nocturnal enuresis patients are all evaluated with physical examination and post void residual check.
- DVQ questionnaire is administered
- Inclusion and exclusion criteria evaluated
- treated with standard urotherapy previously described.

Visit 1:

- Confirm that patient has no daytime voiding symptoms identifying patient has MNE and qualifies for study
- Offer the patient treatment Choices:

2000031281

February 20, 2024

- medical treatment if so no longer candidate for study
- Alarm therapy: If Alarm therapy is chosen: randomize into SNEA or GoGoband®
- Consent to be signed
- Dispense alarm that day or have patient return within a week to have the alarm demonstrated and how to setup and to take home.
- Subject log is given along with alarm.

Visit 2:

- 1 month virtual or in person to follow progress,
- log is handed in, scanned into my chart, faxed or emailed
- new log dispensed

Visit 3:

- 2 month virtual or in person to follow progress
- log is handed in, scanned into my chart, faxed or emailed
- a new log dispensed

Visit 4:

- 3 months virtual or in person to close out study,
- log is handed in, scanned into my chart, faxed or emailed.
- Patients are informed that they can keep the alarm and continue to use it if they wish.

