3.4.3.7 Other

3.4.4 Subsets and Covariates

3.4.5 Handling of Missing Data

Patients who drop out of the study will be considered failures for purposes of the study with regards to success vs partial or failure analysis
 Dry /wet night rates will be maintained for the overall analysis of overall dry/wet ratios regardless of the patient ceases participation

4 Trial Administration

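### Inadequate home internet forces a study exit in the GoGoband arm only; these children should stay in follow-up, and the connection should be confirmed before randomisation

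*Combined protocol and SAP*

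**What the plan says.** All references are to the combined protocol and SAP.

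- **Exit rule.** Section 3.2.1 (Potential Risks) says that "internet service at the home may be inadequate for proper functioning of the GoGoband® alarm, if so, they will need to exit the study". No rule takes an SNEA child out of the study because of the home connection.
- **Eligibility.** Section 5.3.2 applies to both arms: "Subjects to be eligible for the Trial need to have functioning WiFi at home utilizing a home network and not a cellular tethering connection". It gives no device requirement and no method or time of verification.
- **Order of events.** Section 3.3.1 (Study Schedule), Visit 1, lists "If Alarm therapy is chosen: randomize into SNEA or GoGoband" and, further down, "Dispense alarm that day or have patient return within a week to have the alarm demonstrated and how to setup and to take home". No connection check appears before randomisation.
- **Drop-outs, response categories.** Section 3.4.5: "Patients who drop out of the study will be considered failures for purposes of the study with regards to success vs partial or failure analysis". There is no exception for technical exits.
- **Drop-outs, nightly data.** The same section continues: "Dry /wet night rates will be maintained for the overall analysis of overall dry/wet ratios regardless of the patient ceases participation".
- **Device faults, for contrast.** Section 6.1.2: "If a bedwetting alarm breaks or is nonfunctional the device will be replaced, and the study will proceed from the last active day". A hardware fault keeps the child in the study; an internet fault does not.

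**The concern.** Randomisation makes the arms alike in household type, including quality of connection. The exit rule then acts on that characteristic in one arm. A GoGoband child in a home with a poor connection has to leave. An SNEA child in the same kind of home stays and can still be counted as cured.

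Neither way of handling the exits restores the comparison. If they count as failures, the GoGoband success proportion is lowered by a rule that has no SNEA counterpart. If they are excluded, GoGoband is left with well-connected homes while SNEA keeps all homes. The plan does not say plainly which applies: 3.2.1 speaks of exiting, 3.4.5 of dropping out, and 6.1.2 and 3.3.7 of removal. That leaves room for the choice to be made once results are known.

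At stake are the cured, partially better and no-improvement outcomes, which sections 5.2.1 and 3.4.3.1 list among the primary outcomes and analyses. The dry-night rate, which the synopsis names as the primary objective, is affected less.

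**Working it through.** **Inputs from the plan.** Section 3.4.2: SNEA 0.5, GoGoband 0.8, ratio 1, one-sided 5%, power 0.80, stated sample size 29. Section 5.3.1: 50 per group (the synopsis gives 150 in total; the 50 per group also matches the envelopes in 6.1.2).

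**Assumed.** The share f of the GoGoband arm that exits for internet reasons is not in the documents; 2% to 20% is shown. Exiting children are taken to have the same underlying success probability as the rest of their arm, and the SNEA proportion stays at 0.5. Section 3.4.2 does not name the outcome behind 0.5 and 0.8; they are read here as proportions of children who succeed.

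**Step 1: reproduce the plan's figure.** One-sided, unpooled variance:

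n = [0.5×0.5 + 0.8×0.2] × [(1.645 + 0.842)/0.30]² = 0.41 × 68.70 = 28.2, rounded up to 29.

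This matches the stated 29 and shows that it is a per-group number.

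**Step 2: effect on the success proportion.** With exits counted as failures, the GoGoband proportion becomes 0.8 × (1 − f).

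**Step 3: power at 50 per arm.** With x SNEA and y GoGoband successes and p̄ = (x + y)/100, the test statistic is z = [(y − x)/50] / √[2p̄(1 − p̄)/50]. Power is the exact binomial probability, summed over all pairs (x, y), that z exceeds 1.645. The last column repeats the Step 1 formula with the reduced proportion.

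| f | GoGoband proportion | Difference from 0.5 | One-sided power, 50 per arm | n per group for 80% power |
|---|---|---|---|---|
| 0% | 0.800 | 0.300 | 94.7% | 29 |
| 2% | 0.784 | 0.284 | 92.1% | 33 |
| 5% | 0.760 | 0.260 | 86.8% | 40 |
| 10% | 0.720 | 0.220 | 73.9% | 58 |
| 20% | 0.640 | 0.140 | 39.8% | 152 |

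Power is 81.0% at f = 7.5% and 79.6% at f = 8%, so it crosses the planned 80% at about 8%, or 4 children in 50 (0.08 × 50).

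**Step 4: equally effective devices.** If both had a true success proportion of 0.5, exits alone would give an apparent difference of 0.5(1 − f) − 0.5: −0.025 at 5%, −0.05 at 10% and −0.10 at 20%, all against GoGoband.

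**Step 5: dry-night rate.** Under the second sentence of 3.4.5, observed nights are kept and none is imputed as wet. The exit shortens the GoGoband record only. Its effect cannot be calculated, because neither the number nor the timing of exits is given.

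**The case against.** The strongest case for leaving the plan alone has five parts.

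1. **WiFi is already screened.** Section 5.3.2 requires functioning home WiFi in both arms and rules out tethering, so only a remainder can exit. This stands as a reason to expect a low rate. It does not close the gap: functioning is not the same as adequate for the device, and 3.2.1 itself still treats inadequate internet as a risk.
2. **Inadequacy might be found before randomisation.** Eligibility is reviewed before study entry, and the appendix list includes prescreening questions whose content is not shown. This stands in part. The documents do not show that inadequacy is always found late; they show that nothing listed prevents it.
3. **Counting exits as failures is defensible.** A device that cannot work in an eligible home has failed there, and the rule is conservative for the superiority hypothesis in 4.1. Both are fair. But the plan does not state that reasoning, it would not justify ending follow-up, and the objective in 4.2 asks whether GoGoband is as effective or more effective, so a bias against it can hide a real result.
4. **The failure rule does not reach every outcome.** Correct. A reader might infer from "Patients who drop out of the study will be considered failures for purposes of the study" that each exit is a GoGoband failure throughout. The rest of that sentence limits it to the response categories, and the next sentence keeps observed nights.
5. **The larger rates are hypothetical.** Correct. Nothing in the documents supports 10% or 20% in particular.

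**Conclusion.** The concern holds in a limited form. The plan allows an avoidable loss after randomisation in one arm only, and does not spell out how it is analysed. On the natural reading it lowers GoGoband success in the cured/partial/failure analysis; for the dry-night rate it only truncates GoGoband nights.

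The size is unknown because the exit rate is unknown. On the plan's own one-sided test at 50 per arm, exits up to about 7.5% leave power above 80%; from about 8% it is below. This rests on 0.5 against 0.8 being success proportions, on exits being counted as failures, and on exiting children being otherwise typical of their arm.

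Two stronger readings should be resisted. A reader might infer that even 5% exits defeat the planned power. That follows only from a two-sided 5% test (78.0% by the same enumeration); section 3.4.2 plans a one-sided test, under which power is 86.8%. A reader might also infer that the rule flatters GoGoband. Counting exits as failures works against it, and excluding them is not what 3.4.5 says about drop-outs.

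**What to change.** 1. **Keep the children in the study (main change).** In 3.2.1 (Potential Risks), replace the mandatory study exit with continued follow-up. Children with connection trouble continue the nightly logs, which the Efficacy section under Assessments already requires in both arms, and are analysed in the assigned arm by their recorded outcomes. Section 3.4.5 should say this explicitly, so that a connection problem is not itself a drop-out. This concerns study participation and analysis only; it says nothing about what treatment the child should receive.
2. **Confirm the connection before assignment.** In 5.3.2, define adequate home WiFi by the device's connection requirement and confirm it for every family before the envelope is opened. The documents state no such requirement, so the sponsor must supply it.

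The second change does not replace the first: a connection that passes at entry can still fail during the 90 days.

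**Cost.** Amended wording in three sections and a connection check before Visit 1 randomisation, which adds a step because the connection to be tested is at home. A few families will be screened out, and the results will apply to homes that pass the check. The logs needed for follow-up are already in the plan.
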